#### **ABSTRACT**

Invasive fungal infections (IFI) have steadily increased over the past 2 decades in children with acute myeloid leukemia (AML). Over 50% of infectious-related deaths in this population are attributable to IFI. These dismal numbers are despite empiric therapy and treatment with the best available agents. The failure of these strategies to impact morbidity and mortality from IFI makes a strong case for the exploration of preventive strategies. This study will utilize a 2-arm, open-label randomized design to evaluate the efficacy of prophylaxis with caspofungin in comparison with fluconazole in children with *de novo*, relapsed or secondary AML. Study agent will begin following completion of each course of chemotherapy and continue through periods of neutropenia. This study also seeks to evaluate the usefulness of the Platelia EIA Aspergillus galactomannan (GM) assay as well as beta-D glucan testing in early diagnosis of IFI. ACCL0933 will also explore the relationship between proven or probable IFI and single nucleotide polymorphisms (SNP) of genes involved in immunity and develop predictive models of IFI that will be useful in the early identification of susceptible patients.

**EXPERIMENTAL DESIGN SCHEMA**

\*Protocol therapy must begin within 24-72 hours following the completion of the first course of systemic chemotherapy for current diagnosis.

# Prophylaxis started within 24-72 hours following completion of each systemic chemotherapy course and continues until ANC > 100-500/ $\mu$ L following the nadir.

^ Galactomannan and beta-D glucan testing twice weekly. See Section 13 for details.

@ SNP- Single Nucleotide Polymorphisms. Collect sample at end of Course 1. See Section 14 for details.

IFI – Invasive Fungal Infections (including Invasive Aspergillosis)

HSCT – Hematopoietic Stem Cell Transplantation

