Posaconazole is an attractive agent to consider as antifungal prophylaxis in the AML population. A randomized, multi-center study of posaconazole vs. fluconazole or itraconazole in patients with neutropenia associated with the treatment of AML or myelodysplastic syndrome found that posaconazole reduced the rate of IFI from 8% to 2% compared to fluconazole. However, children less than 13 years of age were excluded and the median age of study subjects was approximately 50 years of age. Its use is limited in children because of insufficient dosing information for young children. Furthermore, posaconazole has the same concerns regarding hepatotoxicity and drug interactions as exist for voriconazole. Finally, posaconazole can only be administered as an oral agent currently and children receiving AML therapy may not be able to comply with oral medication during the neutropenic period. Therefore, posaconazole is not an appropriate agent to use in children with AML at this time.

The next COG Phase 3 AML trial will randomize subjects to receive or not receive bortezomib and there is considerable risk of drug interactions with concurrent administration of bortezomib and either voriconazole or posaconazole, thus further decreasing the feasibility of their use in pediatric AML.

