## 4.0 TREATMENT PLAN

Timing of protocol therapy administration, response assessment studies, and surgical interventions are based on schedules derived from the experimental design or on established standards of care. Minor unavoidable departures (up to 72 hours) from protocol directed therapy and/or disease evaluations (and up to 1 week for surgery) for valid clinical, patient and family logistical, or facility, procedure and/or anesthesia scheduling issues are acceptable per COG administrative Policy 5.14 (except where explicitly prohibited within the protocol).

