### 4.1 Overview of Treatment Plan

This is a randomized clinical trial designed to assess the efficacy of caspofungin for preventing IFI (including IA) compared to fungal prophylaxis with fluconazole, the standard of therapy used in most COG institutions as prophylaxis in patients with AML and chemotherapy-induced neutropenia.

Patients who consent to participate in ACCL0933 will be randomly assigned to antifungal prophylaxis with either fluconazole or caspofungin. Treatment with any anti-fungal prophylaxis after enrollment must be terminated prior to starting protocol-directed anti-fungal therapy. Protocol prophylaxis will be started within 24-72 hours following the last dose of systemic chemotherapy for each course. Administration of antifungal prophylaxis for each course will continue until (a) The absolute neutrophil count (ANC) is  $> 100-500/\mu\text{L}$  following the nadir; *OR* (b) Start of the next chemotherapy course; *OR* (c) Patient meets any off-protocol criteria (Section 8.1).

If other systemic antifungal therapy is initiated for empiric therapy or treatment of suspected infection, then protocol prophylaxis should be held and assigned prophylaxis should resume when other systemic antifungal therapy is discontinued if this occurs prior to ANC recovery.

Administration of assigned systematic antifungal prophylaxis continues with subsequent courses of chemotherapy until the patient meets any off-protocol criteria including proven or probable IFI according to institutional diagnosis.

Fluconazole may be administered either intravenously (IV) or orally. Caspofungin is only available as an IV formulation.

**Note** - For those institutions where patients are discharged prior to ANC recovery to  $100-500/\mu\text{L}$  the following options exist:

- If the patient has been randomized to fluconazole they can continue this therapy orally at home until the ANC is  $>100-500/\mu\text{L}$ .
- If the patient is on caspofungin the parents and patient can decide to either remain in the hospital to continue caspofungin until the ANC is  $> 100-500/\mu\text{L}$  or be discharged home on daily IV caspofungin therapy until the ANC is  $> 100-500/\mu\text{L}$ . The latter may be associated with home healthcare costs that would not be funded by the study. It should be confirmed prior to discharge that the insurance company or other sources will cover such home healthcare costs.

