- If the insurance company or other sources will not cover home healthcare costs not funded by the study, then the family can elect to pay for these services themselves or go home without continued caspofungin prophylaxis. In this circumstance, the treating physician should proceed with their standard clinical practices.

See Section 6.2 for information regarding investigational vs. commercial drug supply following discharge home.

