The assumed baseline incidence of IFI of 8% at 5 months is based on data reported in previous studies. CCG protocol 2961 found a 13% incidence of IFI. The rate of microbiologically documented sterile site fungal infections documented on AAML0531 is  $12 \pm 2\%$  as of April 2010; not all of these would meet MSG/EORTC criteria as proven/probable IFIs. In the power calculation, the onset of IFI in both groups over the 5-month period is assumed to follow an exponential distribution and is 8% and 2% for fluconazole and caspofungin at 5 months respectively. Under such exponential models, the incidence of over 5 months is approximately even, about 1.6% per month for fluconazole and 0.4% per month for caspofungin.

In this setting, we have a potential competing risk issue but its impact on estimating the risk for IFI should be minimal. We expect that majority of the censoring for IFI prior to the study completion are due to SCT or relapsed/refractory disease; the occurrence of such events are likely independent of the risk for IFI should the patient continue on the AML therapy, and can be considered true censoring events in the power consideration above. On the other hand, death prior to any other event constitutes a competing risk for IFI, but we expect such deaths to be rare and will not likely exceed 5% during the first 5 months; the impact that it has on estimating the risk of IFI by treating it as censored is minimal. Recently there have been some developments on sample size considerations under competing risk setting for either the

proportional cause-specific hazard model or proportional sub-distribution hazard model. However since the cumulative incidence of IFI under competing risk setting also involves the cause specific hazard of the competing risk, the interpretation of some of the planning parameters in these settings can be complicated and additional assumptions about the competing risk need to be made; it is also not yet well understood which model is better in different real settings. Given the fact that the true competing risk here is rare, we still use standard survival analyses for sample size considerations, but will perform competing risk analyses on the study data to ensure that it does not change the results of the comparison.

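### The prophylaxis stopping rule is a range of neutrophil counts, so in an open-label trial the length of cover can differ by arm without a deviation

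*Combined protocol and SAP*

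**What the plan says.** The schema has prophylaxis begin 24-72 hours after "completion of each systemic chemotherapy course and continues until ANC > 100-500"/µL following the nadir. Sections 4.1, 4.2 (fluconazole) and 4.3 (caspofungin) give the same range. A course also ends at the next chemotherapy course or when an off-protocol criterion is met. The two delivery maps refer back to 4.2 and 4.3.

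Section 4.1 then treats the arms differently at early discharge. The note opens "For those institutions where patients are discharged prior to ANC recovery to" 100-500/µL. For one arm: "If the patient has been randomized to fluconazole they can continue this therapy orally at home until the ANC is" above the range. For the other: "If the patient is on caspofungin the parents and patient can decide to either remain in the hospital to continue caspofungin until the ANC is" above the range, or take daily intravenous caspofungin at home. The study does not fund the home healthcare costs that may arise, although an insurer may. If nobody else pays, "then the family can elect to pay for these services themselves or go home without continued caspofungin prophylaxis".

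Three other provisions bear on the point:
- Section 9.1 describes the trial as open-label.
- Section 9.3.1 counts empiric antifungal therapy only when it is started while the patient is on prophylaxis.
- Section 9.3.4 analyses by assigned arm, whatever the compliance.

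**The concern.** Length of cover is part of what is being compared. Stopping just above 100/µL and stopping just above 500/µL both comply. The first patient still has a count below the 500/µL that the Appendix II host factor uses to define neutropenia.

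If every site held to one value, randomization would balance it between arms. Nothing requires that, and the person choosing within the range knows the arm and faces an unequal burden of continuing. Blinded endpoint review (Section 9.3.2) protects the classification of infections. It does not govern when drug is stopped.

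Two things are at stake:
- **Interpretation of the primary comparison.** If caspofungin were stopped earlier, the likely effect is dilution, and a null result would be harder to read as a statement about the drug.
- **The empiric-therapy endpoint.** An arm with shorter courses has less time in which an empiric start can count, whatever the drug does. Analysis by assigned arm does not correct this.

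**Working it through.** **1. Is one value fixed anywhere?** The schema and Sections 4.1, 4.2 and 4.3 give only the range. Sections 7.1 and 13.1.2 use the same range to bound the neutropenic period for sampling. Section 4.1 makes resumption after empiric therapy depend on ANC recovery, again without a number. Randomization is stratified by disease group only. So the discretion exists, and it is open to use by arm.

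**2. Can the direction be predicted?** No.
- Toward shorter caspofungin: the route and discharge provisions in 4.1.
- Toward shorter fluconazole: Section 2.2.2.1 says, when discussing posaconazole, that "children receiving AML therapy may not be able to comply with oral medication during the neutropenic period". Section 5.2 holds fluconazole at ALT or AST above 5 times ULN or bilirubin above 2 times ULN, but holds caspofungin only at a Child-Pugh score above 9.

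**3. The plan's own power figure (Section 9.3.3).** Inputs: 8% against 2% IFI at 5 months, 275 per arm, 35% censored by 5 months, exponential failure and censoring, two-sided 0.05 log-rank.
- Monthly hazards: λF = −ln(0.92)/5 = 0.01668; λC = −ln(0.98)/5 = 0.00404; censoring c = −ln(0.65)/5 = 0.08616.
- HR = 0.00404/0.01668 = 0.242 (plan: 0.24).
- Expected events per arm = 275·λ/(λ+c)·(1 − exp(−5(λ+c))): 17.9 + 4.5 = 22.4.
- Freedman: z = √22.4·(1−0.242)/(1+0.242) − 1.96 = 2.887 − 1.96 = 0.927, power 82%. Simulated log-rank power is 86%. The plan's figure of about 80% is reproduced closely enough.

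**4. A one-directional what-if, not an estimate.** The documents give no number of days between ANC 100 and 500. Suppose every caspofungin patient lost 1, 2 or 3 days in every course, fluconazole lost none, and each lost day carried the full fluconazole-arm hazard. With f the share of risk lost, the caspofungin hazard is λC + f(λF − λC).
- Table 2 (Section 13.4): courses per patient = (440+380+337+216)/440 = 1373/440 = 3.12. Neutropenic days per patient = (440·20 + 380·18 + 337·17 + 216·28)/440 = 27417/440 = 62.3.
- Share lost per one-day gap: 3.12/152.2 = 2.05% if risk is even over 5 months, as Section 9.3.3 assumes ("Under such exponential models, the incidence of over 5 months is approximately even"); 3.12/62.3 = 5.0% if all risk falls on neutropenic days.

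| Days lost per course | Even incidence: f, HR, power | Neutropenic days only: f, HR, power |
|---|---|---|
| 0 | 0, 0.242, 86% | 0, 0.242, 86% |
| 1 | 2.1%, 0.258, 84% | 5%, 0.280, 81% |
| 2 | 4.1%, 0.273, 81% | 10%, 0.318, 74% |
| 3 | 6.2%, 0.289, 79% | 15%, 0.356, 67% |

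Power is simulated, 20,000 trials per row, without interim looks. On the plan's own model even three days leaves power close to the stated 80%. The larger losses appear only when that model is replaced. Table 2 does not say what ANC threshold defines its durations, so the 62.3 days cannot be tied to the 100-500 window. Earlier stopping of fluconazole is not computed, because the documents give no comparable rate without prophylaxis.

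**The case against.** The range is deliberate. It appears in identical form for both arms, and the discharge note in 4.1 treats count-recovery practice as an institutional matter. A difference arises only if sites choose by arm, and nothing shows that they do. This stands: the text shows that cover can differ, not that it will.

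The burden of caspofungin should not be overstated. Section 4.1 says that insurers or other sources may cover home care. Section 6.2 has the manufacturer supply the drug and limits commercial stock to home use where local rules bar dispensing study drug. For a patient kept in hospital until recovery, the discharge cost does not arise.

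Two other routes to shorter cover do not depend on the range. One is going home without caspofungin. The other is Section 4.0, which accepts "Minor unavoidable departures (up to 72 hours) from protocol directed therapy and/or disease evaluations". Both survive any declared value.

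Section 9.3.4 already plans descriptive statistics by arm for all measured variables, and the delivery maps record end dates and held doses. Much of the reporting is therefore already provided for. Infections after early stopping still count, because Section 8.3 keeps patients under observation.

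A reader might infer from the table that the trial is underpowered. The documents do not support that. The gaps come from no section, run one way, and apply to every patient and course. If one course in four had a 2-day gap, the mean loss would be 0.5 day per course. Interpolating gives about 85% (even incidence) or 83% (neutropenic days only), both above the stated 80%.

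None of this removes the freedom to choose by arm inside the range.

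**Conclusion.** The point holds as a cheap improvement to the protocol, not as a threat to validity. The rule leaves the end of each course open between 100 and 500/µL, and in an open-label trial with unequal burden that choice may depend on the arm. The consequences would be some mixing of drug effect with length of cover, and an unequal window for the empiric-therapy endpoint. The size is unknown, the sign could be either, and the difference may be zero.

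Three stronger readings are not supported:
- That caspofungin will be stopped earlier: provisions point both ways.
- That the primary analysis is biased: intention to treat remains a valid comparison of the two strategies as delivered.
- That recovery from neutropenia in 8.1(e) and 8.3(c) is a separate undefined term: Sections 4.1, 7.1 and 13.1.2 tie it to the same range, so it only needs to follow whatever value is chosen.

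**What to change.** - In Sections 4.1-4.3 add: *Before its first enrolment each institution declares one ANC value within 100-500/µL and applies it to all its patients in both arms.*
- Use that declared value for ANC recovery in 4.1-4.3 and, by cross-reference, for recovery from neutropenia in 8.1(e) and 8.3(c).
- Within the descriptive analyses of 9.3.4, name prophylaxis days per course by arm, with days held shown separately, and a count of patients discharged without caspofungin.

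**Cost:** one sentence, one cross-reference, one declaration per site, and one named table from data that the delivery maps already record. Sample size and primary analysis do not change. Clinicians lose per-patient discretion within the range, while institutional practice is kept. The go-home option and the 72-hour allowance remain, so differential stopping is reduced, not removed. The table would show what is left.

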## 1.0 GOALS AND OBJECTIVES (SCIENTIFIC AIMS)

### 1.1 Primary Objective

#### 1.1.1

To determine if prophylaxis with caspofungin administered during periods of neutropenia following chemotherapy for acute myeloid leukemia (AML) is associated with a lower incidence of proven or probable invasive fungal infections (IFI) compared with fluconazole.

### 1.2 Secondary Objectives

#### Clinical

#### 1.2.1

To determine if prophylaxis with caspofungin will result in a lower incidence of proven or probable cases of invasive aspergillosis (IA) compared with fluconazole.

#### 1.2.2

To determine if prophylaxis with caspofungin will result in improved survival compared to fluconazole.

#### 1.2.3

To determine if prophylaxis with caspofungin will result in less empiric antifungal therapy compared to fluconazole.

#### Biological

#### 1.2.4

To determine the sensitivity, specificity, positive and negative predictive value of biweekly galactomannan (GM) and beta-D glucan testing in diagnosing IFI.

#### 1.2.5

To test the association between single nucleotide polymorphisms (SNPs) in genes involved in innate immunity and proven or probable IFI.

#### 1.2.6

To develop predictive models of IFI using SNP in genes involved in immunity and clinical covariates.

## 2.0 BACKGROUND

### 2.1 Overview and Rationale for Study

This study is a 2-arm open-label randomized clinical trial to evaluate the efficacy of caspofungin prophylaxis compared with fluconazole prophylaxis. A total of approximately 550 subjects will be randomized (until accrual of at least 275 participants on each treatment arm) during periods of neutropenia associated with chemotherapy for the treatment of AML.

The frequency and severity of IFI in immunocompromised patients has increased steadily over the past 2 decades. The incidence of IFI as a cause of sepsis has more than tripled with 5,231 cases in 1979 compared with 16,042 cases in 2000. In children with fungal sepsis, the case fatality rate has been estimated to be 13%. Among children with cancer, those undergoing hematopoietic stem cell transplantation (HSCT) and those receiving AML therapy are at highest risk for IFI. The most common

causes of IFI in children with cancer are *Candida* spp. and *Aspergillus* spp.

*Candida* spp. are commensal organisms that normally reside on mucosal and skin surfaces. The portal of entry is typically the gut mucosa and less commonly the skin. Therefore, children undergoing intensive therapy for cancer that results in mucositis are at high risk for infection with *Candida* spp. Although mucosal candidal infections occur, candidemia is the most serious clinical syndrome caused by *Candida* spp. Its manifestations may include fever unresponsive to antibiotics, macronodular skin lesions, myalgias, and sepsis. Acute hematogenous dissemination of *Candida* to 1 or more organs can occur including the heart, lung, brain, eye, kidney, liver and spleen. Immunocompromised children are at higher risk for disseminated disease. Disseminated infections are considered to be more severe and require longer courses of antifungal therapy. The attributable mortality of invasive candidiasis in children has been reported to be 10%. These data suggest that 1 child would be saved for every 10 children in whom candidemia can be prevented.

Infections with *Aspergillus* spp. account for the vast majority of non-*Candida* IFI in children with cancer. Children undergoing AML therapy have the highest risk of IA outside the transplant setting. IA most commonly presents as pneumonia. Infiltrates are commonly wedge-shaped, pleural-based or nodular and visible on chest radiographs or CT scans. The infiltrates may initially be accompanied by a halo sign and later by a crescent sign. In children with uncontrolled infection, the infiltrates may be diffuse. Less commonly, sinusitis may also occur. Finally, *Aspergillus* can disseminate to the central nervous system. IA is associated with mortality rates in children of greater than 50%.

The burden of IFI in pediatric AML is considerable. CCG 2961 demonstrated that the incidence of IFI in children with AML was 13% per treatment phase. Approximately half the infections were caused by *Aspergillus* and the other half by *Candida*. Most importantly, 31% of infection-related deaths were associated with *Aspergillus*, and 25.9% of infectious deaths were associated with *Candida*. In order to impact on survival of children with AML, strategies to reduce IFI are urgently needed. In general, the 3 types of strategies directed toward fungal infections are prophylaxis, empiric therapy, and treatment of IFI. The current rates of IFIs and attributable mortality due to IFI are primarily derived from the setting of empiric therapy and treatment with best available agents, and thus, these strategies currently are insufficient to make a major impact on fungal morbidity and mortality. Thus, strategies to prevent IFI should be the priority. Furthermore, IFIs likely impact on the ability to deliver anti-leukemic therapy and many IFI are never microbiologically documented, further strengthening the imperative to prevent IFI rather than relying upon empiric or treatment strategies alone.

## 2.2 Selection of Study Medication

### 2.2.1 Choice of Fluconazole Prophylaxis as the Standard Arm

A systematic review and meta-analysis of randomized, clinical trials demonstrated antifungal prophylaxis significantly decreased all-cause mortality in patients receiving chemotherapy. The conclusions from the systematic review and consensus guidelines from the Centers for Disease Control and Prevention, the Infectious Disease Society of America, the American Society for Blood and Marrow Transplantation, and the first European Conference on Infections in Leukemia all recommend antifungal prophylaxis for HSCT recipients. The systematic review concluded that antifungal prophylaxis “should probably be administered to high-risk leukemia patients.”

Fluconazole has been shown to be an effective antifungal agent for prophylaxis against IFI in high-risk patients in previous studies and antifungal prophylaxis with fluconazole reduces morbidity and mortality among allogeneic HSCT recipients. Fluconazole has also been used in other patient populations with neutropenia, although its effectiveness in these patients is less clear. However, fluconazole may not be

the best agent for patients with AML since it lacks activity against filamentous fungi (e.g. *Aspergillus*), which represent half the causes of IFI in children with AML.

Nonetheless, the trial uses fluconazole as the standard prophylaxis arm because it is effective against *Candida* infections, and its use as prophylaxis is regarded appropriate by the above mentioned consensus guidelines. The first European Conference on Infections in Leukemia, published in 2007, recommended fluconazole as the preferred agent for anti-fungal prophylaxis. In addition, as highlighted by Wingard, it is not known whether the toxicity and cost of adding empiric mold coverage is superior to a strategy of fluconazole and aggressive monitoring and pre-emptive treatment for molds.

Furthermore, fluconazole was chosen as the comparator as it is the most commonly used agent for antifungal prophylaxis in pediatric AML in North America and according to a recent COG-wide survey, 154/178 (86.5%) of institutions currently use either fluconazole or no prophylaxis in children with *de novo* AML.

Another possible agent which could have been chosen as the control arm is itraconazole. Itraconazole has a wider spectrum of activity than fluconazole, including activity against *Aspergillus* and has been shown to be more effective than fluconazole when used for prophylaxis in patients with neutropenia. However, the clinical usefulness of itraconazole is limited by poor tolerability and bioavailability of the oral formulations.

